All consented patients will be asked to complete a baseline (T1) survey [Attachment 6] that includes: demographic characteristics; breast density risk factors (parity, age at menarche, menopausal status, hormonal contraceptive use, breastfeeding, and age at first birth); Family history of breast cancer; and mammography screening history (approximate lifetime number of mammograms, number of times recalled, number of breast biopsies). The primary outcome measure for Aim 1 is anxiety. Anxiety will be measured using the state anxiety subscale of the State-Trait Anxiety Inventory (STAI). This measure was selected because of its known psychometric properties, its use in the mammography literature, and our own experience with its use in an intervention study involving Latinas attending cancer screening. Additional psychosocial measures will include health literacy, cancer fatalism, self-efficacy to return for mammography at the next screening interval, breast cancer worry, perceived risk of breast cancer using numerical, verbal and comparative estimates, and the Patient-Reported Outcomes Measurement Information System (PROMIS) measure (short form) addressing depressive symptoms. Knowledge will be assessed using two previously developed items for the national survey regarding density as an independent risk factor and as having a masking effect as well as additional items derived from the written education materials. Our selection of short form assessments where available carefully balances capturing a comprehensive set of important psychosocial measures while reducing respondent burden. We have chosen published measures with favorable psychometric properties and use existing measures where available. Administering the depression measure from the PROMIS Initiative (www.nihpromis.org) will utilize an important resource for validated patient-reported outcomes (PROs) and position our study results within a larger, cross-institute NIH initiative. Based on our experience at MPHC, an interviewer-facilitated mode of survey completion is preferred by patients over self-administered surveys and results in higher quality data. We will provide paper surveys in English and Spanish; participants can mark their own answers or follow along and mark their answers as questions are read to them by the CRC. We anticipate the study assessments will take approximately 30 minutes to complete. The study coordinator will review the responses to the PROMIS items related to depression following completion of the T1 survey. Based on the responses, the study coordinator will follow the steps in the Plan for Depression Questions [Attachment 18]. If the plan

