Follow-up (T2) Assessment. Participants will be contacted by study staff using Mayo Clinic or Mountain Park telephone that will display the Mountain Park phone number.[Attachment 8] approximately 2 weeks after patients have their mammogram to complete a follow-up survey [Attachment 9]. If the study staff is unsuccessful in reaching the participant by telephone, the T2 survey will be mailed to the participant with a cover letter [Attachment 10] and return postage-paid envelope. If the patient has not actively refused or withdrawn, or completed the T2 assessment, study staff will attempt to follow-up by telephone. Study staff may also send a certified letter asking the participant to call them and schedule a time to complete the survey (see Attached reminder letter). If telephone and mail contacts are not successful, participants will be coded in RAVE as a non-responder at T2. The CRC will collect the data over the telephone and mark the answers on a paper survey for double data entry by the Survey Research Center (SRC). The CRC will ask questions designed to measure acceptability of the method by which women received their breast density results and satisfaction with the content and clarity. Knowledge will be re-assessed using the same items described in the baseline assessment. Women will be queried about their own breast density as a check that the mailed notification was read and processed. Anxiety, depressive symptoms, perceived risk of breast cancer, self-efficacy, and breast cancer worry measures administered at baseline will be repeated. Behavioral intention to return for a screening mammogram at the recommended interval will also be assessed. All women will be asked if they discussed their breast density with their health care provider. Women with dense breasts will be asked if they discussed supplemental screening options with their health care provider (e.g., breast ultrasound, MRI). Questions will address whether each of these activities occurred, and if not, whether they are pending (requested by the patient). If not requested, intentions regarding these behaviors will be measured. The study coordinator will review the responses to the PROMIS items related to depression following completion of the T2 survey. Based on the responses, the study coordinator will follow the steps in the Plan for Depression Questions [Attachment 18]. If the plan calls for study personnel to contact the patient, she will do so in accordance with the Plan for Depression Questions and using the Script for Depression Questions Follow-up [Attachment 19].

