
Follow-up (T3) Assessment. Participants will be contacted by study staff using Mayo Clinic or Mountain Park telephone that will display the Mountain Park phone number.[Attachment 11] approximately 1 year after patients have received their mammogram results to complete the third survey [Attachment 12]. Reminder calls and a T3 survey mailing with cover letter [Attachment 13] will follow the procedures outlined for the T2 assessment. Study staff may also send a certified letter asking the participant to call them and schedule a time to complete the survey (see Attached reminder letter). Study staff may also approach patients in clinic if they present to the mammography unit for screening.. If telephone, in-person and mail contacts are not successful, participants will be coded in RAVE as a non-responder at T3. The T3 assessment will include repeated measurement of anxiety, depressive symptoms, breast cancer worry, perceived risk, and discussion of their breast density with their health care provider. It will include questions regarding information seeking about the topic of breast density and re-assess breast density knowledge. Intentions regarding future utilization of mammography and supplemental breast screening will be measured. Attendance at mammography will be queried to capture self-reported screening behavior that may have occurred elsewhere and would not be documented in the MPHC EMR; however this is unlikely because many patients receive low-cost mammography through special programs at MPHC. All women will be queried at the T3 assessment about their attendance at mammography; these self-report data

will be corroborated with EMR data. Women who indicate they received a mammogram elsewhere will be asked where and when this occurred. The study coordinator will review the responses to the PROMIS items related to depression following completion of the T3 survey. Based on the responses, the study coordinator will follow the steps in the Plan for Depression Questions [Attachment 18]. If the plan calls for study personnel to contact the patient, she will do so in accordance with the Plan for Depression Questions and using the Script for Depression Questions Follow-up [Attachment 19].

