Aim 1 will compare the percent change in anxiety (STAI) from baseline between the three study groups at one month (T1) and 1 year (T3) following notification. Assuming the percent change may likely range from -100% to +100% (range of 200 percentage points), we conservatively assume a standard deviation of 50 percentage points (range/4) in the percent change measure. We will have 80% power (along with 1.7% type-I error rate) to detect a difference of 9.3 in average percent change between any two of the groups with a two-sample t-test at T2 with 600 per group. At T3, we will have 80% power to detect a difference of 10.6 (466 per group).

The second outcome will be knowledge regarding breast density, measured ordinally as the number correct of 3 key items (range 0-3 correct). This will be tested with pairwise Wilcoxon rank-sum tests, for which the null hypothesis is that the probability of someone answering more items correctly in one group versus another is 0.5 (i.e. equal chance). At T2, with 600 women per group, we will have 80% power (along with 1.7% type-I error rate) to detect a probability of 0.554 or more between any two of the groups. At T3, we will have 80% power to detect a probability of 0.561 (466 per group).

Aim 2 will compare adherence to next routine screening mammogram between the three notification groups. This outcome "adherence to next annual screening" is pertinent to all 2,000 women and will be obtained via EMR. A sample size of 666 in each group will yield 80% power to detect a difference of 9 percentage points between any two of the groups (type-I error rate 1.7%) based on a chi-square test.

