Aim 3 will qualitatively analyze documentation provided by the *promotora* after each patient interaction in the interpersonal study group. Based on the recommendation of Morse,¹¹⁹ we will have ample data from over 600 patient-*promotora* interactions to capture a range of responses. Furthermore, this large sample size will offer the opportunity to qualitatively examine the type of information exchanged for particular subgroups of patients, such as Spanish-speaking only, those receiving notification that they have dense breasts, and those receiving notification that they do NOT have dense breasts. The analysis of Aim 3 qualitative data will provide a rich resource for informing the design of targeted educational materials for specific populations and developing generalizable tools to enhance communication about appropriate risk-based screening for breast cancer.

Data Analysis Plan:

Analytic Approach for Specific Aim 1

This Aim will compare anxiety as well as knowledge gained between breast density notification approaches (usual care, enhanced, interpersonal). Anxiety will be measured using the state anxiety scale within the State Trait Anxiety Inventory (STAI). Items within this scale are rated on a 0 to 3 Likert-type scale and scores are calculated as the sum of the items. The possible scores can range from 0-60, with higher scores indicative of greater anxiety. To adjust for baseline anxiety levels, we will calculate the percent change in anxiety from baseline at each follow-up: $100 * (\text{follow-up anxiety} - \text{baseline anxiety}) / \text{baseline anxiety}$. We hypothesize that there will be less increase in anxiety for the interpersonal group as compared to the enhanced or usual care groups. The percent change will be compared between the three notification study groups with pairwise t-tests at one month as well as at one year following notification. To account for three pairwise comparisons within each time point, P-values less than 0.017 will be considered statistically significant, to preserve an overall type-I error rate of 0.05 within each time point.

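### The Aim 1 primary anxiety outcome, percent change on a 0–60 score, is undefined at a baseline of 0, does not adjust for baseline, and rests on an SD of 50 that is not shown to be conservative

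*Combined protocol and SAP*

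**What the plan says.** The Methods paragraph on the baseline (T1) survey names the outcome: "The primary outcome measure for Aim 1 is anxiety", measured with the STAI state subscale. Under Analytic Approach for Specific Aim 1, "Items within this scale are rated on a 0 to 3 Likert-type scale and scores are calculated as the sum of the items", and "The possible scores can range from 0-60, with higher scores indicative of greater anxiety".

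The same section gives the outcome and its purpose: "To adjust for baseline anxiety levels, we will calculate the percent change in anxiety from baseline at each follow-up". The formula is 100 × (follow-up − baseline) / baseline. For the test, "The percent change will be compared between the three notification study groups with pairwise t-tests", at each of two follow-up times, with P < 0.017 as the threshold. No baseline covariate is included.

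The Power Statement for Aim 1 sets the SD: "Assuming the percent change may likely range from -100% to +100% (range of 200 percentage points), we conservatively assume a standard deviation of 50". This figure is one quarter of the assumed range. From it the plan derives detectable differences of 9.3 at T2 (600 per group) and 10.6 at T3 (466 per group) with 80% power.

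The documents give no rule for a baseline of 0, no sensitivity analysis for this outcome, and no STAI mean, SD or baseline-to-follow-up correlation.

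**The concern.** Four features of this choice cause trouble.

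1. A woman who scores 0 at baseline has no value on the primary outcome. Without a rule, someone must decide after seeing the data whether to drop or impute her.
2. The planning range of −100% to +100% does not match the formula, which is bounded below at −100% but can go far above +100%.
3. Dividing by baseline does not remove the dependence on baseline. It gives the most extreme values to women with little initial anxiety, who then dominate the variance.
4. The SD of 50 is called conservative without support, and the detectable differences scale directly with it.

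The validity of the between-arm test is not at stake, because randomisation protects it. What is at stake is the power of the trial's first comparison and the meaning of the reported means. The plan's hypothesis concerns a smaller increase in anxiety, and mean percent change can show an increase when average anxiety has not moved.

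**Working it through.** **Inputs from the plan.** SD 50; 600 per group at T2 and 466 at T3; α = 0.017 per comparison; power 80% (Power Statement). Score range 0–60 and the percent-change formula (Analytic Approach for Specific Aim 1). The test is taken as two-sided, which the plan does not state; a one-sided test would give 86–87% power and so does not fit its figures.

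**Step 1: the plan's own figures.** Detectable difference = (z₀.₉₉₁₅ + z₀.₈₀) × SD × √(2/n), with 2.387 + 0.842 = 3.228.
- T2: 3.228 × 50 × √(2/600) = 9.32
- T3: 3.228 × 50 × √(2/466) = 10.57

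Both agree with the plan, so the arithmetic is sound.

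**Step 2: bounds of the formula.** At baseline b the largest possible value is 100 × (60 − b)/b: +500% at b = 10, +200% at b = 20, +100% at b = 30, +50% at b = 40. At b = 0 it is undefined. Only the upper half of the scale stays within the assumed range.

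**Step 3: is range/4 cautious?** Within −100% to +100%, a uniform distribution has SD 200/√12 = 57.7, and the maximum (half the women at each end) is 100. Power for 9.3 points at T2 is Φ(9.3 / (SD × √(2/600)) − 2.387):

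| SD | 40 | 50 | 57.7 | 75 | 100 |
|---|---|---|---|---|---|
| Power | 95% | 80% | 66% | 41% | 22% |

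Power for 10.6 points at T3 is the same to the nearest point.

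**Step 4: behaviour of percent change under assumed score distributions.** The documents give no STAI distribution, so these inputs are assumptions: gamma-shaped baseline and follow-up scores with the same distribution, joined by a normal copula, rounded and limited to 0–60, with baseline-to-follow-up correlation from 0.4 to 0.8.

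| Baseline mean (SD) | SD of percent change, correlation 0.4 to 0.8 | Baseline of 0 |
|---|---|---|
| 10 (8) | 199 to 79 | 1.3% |
| 15 (10) | 149 to 60 | 0.1% |
| 20 (12) | 118 to 50 | about none |
| 25 (10) | 55 to 28 | about none |
| 30 (10) | 42 to 23 | about none |

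Percent change correlated with baseline at about −0.3 to −0.5 in every scenario. The tenth of women with the lowest baselines supplied roughly 21–65% of its variance. Average anxiety did not change in these simulations, yet at correlation 0.4 the mean percent change was about +58%, +30% and +7% at baseline means 10, 20 and 30.

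The share of zeros depends on the assumed shape. With normal scores limited to 0–60 it was about 12% at mean 10 and 0.7% at mean 25.

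**Step 5: power against ANCOVA.** 600 per arm, correlation 0.5, 4,000 replicates, α = 0.017. The effect is a follow-up shift of 9.3% of the baseline mean, or follow-up multiplied by 1.093.

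| Baseline mean | Shift: percent change vs ANCOVA | Proportional: percent change vs ANCOVA |
|---|---|---|
| 10 | 31% vs 46% | 16% vs 41% |
| 15 | 42% vs 64% | 22% vs 60% |
| 20 | 51% vs 75% | 32% vs 70% |
| 25 | 93% vs 99% | 86% vs 98% |
| 30 | 99% vs 99.9% | 97% vs 99.9% |

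Under no effect, both tests rejected at about 1.3–2.1%, close to the nominal 1.7%.

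**The case against.** The strongest reply is that this is a matter of efficiency, not validity. Type I error is intact, and if baseline anxiety averages 25 to 30 the loss is small. Nothing in the documents places this population low on the scale. Zeros may be very rare, and a one-line rule would deal with them. The plan says only that percent change is likely to fall between −100% and +100%, which is an expectation rather than a bound, and range/4 is a common rule for roughly bell-shaped data. SDs of 75 or 100 are sensitivity values, not estimates. Finally, ANCOVA at each visit and a mixed model over both visits are not interchangeable when 10% are expected to be lost by T2 and 30% by T3, so a replacement should name one model.

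Much of this stands as a limit on size. The documents cannot show that SD 50 is too small, and a count of simulated scenarios above 50 would reflect only the grid chosen. The point about naming one model is right.

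It does not rescue the outcome. A rule for zeros would complete the definition but leave the baseline dependence, and baseline adjustment is the only reason the plan gives for using percent change. Even when the effect is proportional, which should suit the metric best, percent change had less power in every scenario tried. The word conservative still has nothing behind it.

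**Conclusion.** The concern holds and should be fixed before the analysis. Three conclusions follow from the plan's text and algebra alone: the primary outcome is undefined at a permitted score with no rule for it; its ceiling passes +100% for any baseline below 30; and nothing in the documents supports calling SD 50 conservative.

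That percent change stays tied to baseline, and costs power, was shown by simulation. The direction was the same in every scenario, but the size depends on the unknown STAI distribution. At baseline means of 10 to 20 the power deficit against ANCOVA was about 15 to 24 points for a constant shift; at mean 30 it was about 1 point. The detectable differences of 9.3 and 10.6 are correct arithmetic on an unsupported SD. No inflation of type I error is claimed.

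**What to change.** Replace the percent-change test under Analytic Approach for Specific Aim 1 with wording such as:

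> The STAI state score at T2 and at T3 will each be compared between arms by linear regression (ANCOVA) with arm and baseline STAI score as covariates. Each of the three pairwise differences will be reported in STAI points with a confidence interval and tested at P < 0.017 within each time point.

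This keeps the plan's separate tests at each time point and retains women who score 0 at baseline. A single baseline-adjusted mixed model over T2 and T3 would also serve, and would use T2 data from women missing at T3. Whichever is chosen should be named as the one primary analysis.

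In the Power Statement, drop the claim that the SD is conservative and give the detectable difference in STAI points over a stated range of SD and correlation, using 3.228 × SD × √(1 − r²) × √(2/n). As an illustration with assumed values:
- T2: from 0.89 points (SD 8, r = 0.8) to 2.05 points (SD 12, r = 0.4)
- T3: from 1.02 to 2.33 points for the same pairs

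Percent change may stay as a descriptive summary for women with a baseline above 0.

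The cost is SAP wording and a restated power figure. No new data or participants are needed: the score is taken at baseline, and the follow-up sections provide for it at T2 ("Anxiety, depressive symptoms, perceived risk of breast cancer, self-efficacy, and breast cancer worry measures administered at baseline will be repeated") and at one year ("The T3 assessment will include repeated measurement of anxiety").

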The study will be conducted at MPHC in the mammography suite. The mammography suite is equipped to screen one patient at a time; there is ample space in the unit for research activities to take place. We will attempt to make pre-recruitment phone calls to women on the screening mammography patient logs, alerting them to a possible study opportunity on the day of their appointment, and to enable them to plan for a little extra time at the clinic if they think they may be interested in participating [Attachment 1]. Women entering the mammography suite will be given a study brochure [Attachment 2a] and if receptive, complete a brief screener to determine study eligibility [Attachment 2b]. The study will be introduced to the patient prior to undergoing mammography by a trained Spanish/English bilingual clinical research coordinator (CRC). If the patient is willing to participate, she will be asked to provide written informed consent [Attachment 3] and authorization to release medical records [Attachment 4] for this research study. She will then be randomized to one of the three notification approaches (study groups) – usual care, enhanced/written education [Attachment 5], interpersonal.

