
calls for the principal investigator to contact the patient, she will do so in accordance with the Plan for Depression Questions and using the Script for Depression Questions Follow-up [Attachment 19].

Additional data will be abstracted from the MPHC EMR [Attachment 7] including: body mass index, breast density category, screening mammogram results (normal or abnormal), and attendance and outcome of any additional/supplemental breast screening (breast ultrasound, MRI, etc.), or breast procedures (breast biopsy). These additional data will position our study to contribute to understanding risk profiles for breast cancer among Latinas and inform risk-based screening.

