We will manage the study data using RAVE and REDCap databases designed specifically for the study. These systems are located behind the Mayo Clinic firewall. Users must have a Mayo Clinic provided ID/password to connect to the databases and their ID must be specifically authorized in order to access study data. Only the PI can grant such authorization. The tools are HIPAA-compliant, can be set up to use branching logic and field validation to help improve the accuracy of data entry, and the data can be easily exported for statistical analysis. Administration of survey assessments (T1, T2, and T3) will occur by telephone and be interviewer-facilitated by the bilingual CRC. Surveys will be

kept secure in a locked file cabinet until they are sent in batches to Rochester for data entry by the Survey Research Center.

(1a) This is a multisite study involving Mayo Clinic and non Mayo Clinic sites. *When checked, describe in detail the research procedures or activities that will be conducted by Mayo Clinic study staff.*

(1b) Mayo Clinic study staff will be engaged in research activity at a non Mayo Clinic site. *When checked, provide a detailed description of the activity that will be conducted by Mayo Clinic study staff.*

The study will be conducted at Mountain Park Health Center and Mayo Clinic Staff will be consenting and following the patient throughout the study through patient contact and through medical records.

Subject Information

Target accrual is the proposed total number of subjects to be included in this study at Mayo Clinic. A "Subject" may include medical records, images, or specimens generated at Mayo Clinic and/or received from external sources.

Target accrual: 2,000

Subject population (children, adults, groups): Adult women presenting for a screening mammogram

Inclusion Criteria:

Speak English or Spanish

Women between the ages 40 and 74

Exclusion Criteria:

Age less than 40 or 75+

Research Activity

Check all that apply and complete the appropriate sections as instructed.

- Drug & Device:** Drugs for which an investigational new drug application is not required. Device for which (i) an investigational device exemption application is not required; or the medical device is cleared/approved for marketing and being used in accordance with its cleared/approved labeling. (Specify in the Methods section)
- Blood:** Collection of blood samples by finger stick, heel stick, ear stick, or venipuncture.

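### The Aim 1 anxiety comparison is a valid average over all women notified, but it makes no use of density category or mammogram result, which are already collected and decide what each woman is told

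*Combined protocol and SAP*

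**What the plan says.** - **Aim 1 test** (Analytic Approach for Specific Aim 1): "The percent change will be compared between the three notification study groups with pairwise t-tests", at one month and at one year, with a threshold of 0.017. The only adjustment is for baseline anxiety, through the score itself: "To adjust for baseline anxiety levels, we will calculate the percent change in anxiety from baseline at each follow-up".
- **Who is pooled** (Subject Information): "Adult women presenting for a screening mammogram", aged 40 to 74, with no restriction by density or result.
- **Timing** (Methods): "The study will be introduced to the patient prior to undergoing mammography". Consent and then randomization follow. No stratification factor is named.
- **What is collected** (Methods, EMR abstraction): "breast density category, screening mammogram results (normal or abnormal" and later procedures.
- **Where density or result is used.** The Aim 3 paragraph of the Power Statement names, among its qualitative subgroups, women told they are dense and "those receiving notification that they do NOT have dense breasts". The Methods also ask women with dense breasts about supplemental screening, record its uptake among them, and examine follow-up delay among recalled women. None of this enters the anxiety comparison. Covariate adjustment appears only under Exploratory Aims 2 and 3.

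**The concern.** The three arms differ in how the density result is communicated. The result itself comes from the mammogram. Density category and normal/abnormal status can therefore serve as covariates or subgroup factors, even though they become known after randomization.

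Two things are lost by leaving them out:

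- **Precision.** Any variation in anxiety that follows from the result stays in the error term.
- **Interpretation.** Being told one's breasts are dense and being told they are not are different messages. A single pooled contrast does not show where an effect lies. If the effect were confined to one group, the pooled estimate would be diluted, and any later breakdown by density would be post hoc.

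The documents lend some weight to density as a source of anxiety: the Background reports that 59% of Hispanic women in the national survey agreed or strongly agreed that they felt anxiety about learning their own density. They give no corresponding figure for recall.

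**Working it through.** **Inputs from the Power Statement.** SD 50 percentage points; 600 per group at T2 and 466 at T3; type-I error 0.017; power 80%. Sidedness is not stated; a two-sided test reproduces the figures.

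**Plan's own figure.** Detectable difference = SD × √(2/n) × (z for 1 − 0.017/2 + z for 0.80), and 2.387 + 0.842 = 3.228.
- T2: 50 × √(2/600) × 3.228 = 2.887 × 3.228 = 9.32 (stated 9.3).
- T3: 50 × √(2/466) × 3.228 = 3.276 × 3.228 = 10.57 (stated 10.6).

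The pooled power statement is arithmetically sound.

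**Precision from adjusting for recall (assumed inputs).** With recall share p and a shift of d total SDs in the outcome, the fraction of variance explained is R² = p(1 − p)d². The equivalent extra women per group are 600/(1 − R²) − 600, and the adjusted detectable difference is 9.32 × √(1 − R²).

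| p | d | R² | Extra women per group, T2 | Detectable difference, T2 |
|---|---|---|---|---|
| 5% | 0.5 | 1.2% | 7 | 9.3 |
| 10% | 0.5 | 2.3% | 14 | 9.2 |
| 10% | 1.0 | 9.0% | 59 | 8.9 |
| 15% | 1.0 | 12.8% | 88 | 8.7 |

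At 10% recall, power for 9.3 points rises from 80% to about 81% to 84%. The further gain from adjusting for density is not quantified, because the documents give nothing to base it on.

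**Dilution (assumed inputs).** Suppose a 9.3-point benefit exists only in dense women, with share q, and is zero in the rest. The pooled effect is 9.3q. Pooled power is Φ(9.3q/2.887 − 2.387). The detectable difference within dense women uses n = 600q.

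| q | Pooled effect | Pooled power | Dense women per group | Dense-only detectable difference | Dense-only power for 9.3 |
|---|---|---|---|---|---|
| 30% | 2.8 | 8% | 180 | 17.0 | 27% |
| 40% | 3.7 | 14% | 240 | 14.7 | 36% |
| 50% | 4.7 | 22% | 300 | 13.2 | 46% |
| 70% | 6.5 | 45% | 420 | 11.1 | 62% |

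**Interaction.** The detectable arm-by-density difference at two-sided 0.05 is 50 × √(2/(600q) + 2/(600(1 − q))) × (1.960 + 0.842). This is 16.2 points at q = 50%, 16.5 at 40% and 17.7 at 30%.

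**The case against.** The case for leaving the analysis alone is substantial.

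- **Validity.** Randomization keeps the unadjusted contrast unbiased and its type-I error intact. A reader might infer that the pooled comparison is biased, or that it cannot answer the trial's question. The documents do not support either. The opening section asks about the law's impact on patients receiving mammography, and Aim 1 compares approaches among Latinas generally, so the average over dense and non-dense women is what the plan sets out to estimate.
- **Timing.** A reader might also fault randomization before the result is known. It is not a fault: approaching women before the mammogram allows baseline STAI to be taken before any result.
- **Recall.** It is tempting to say that recall dominates anxiety at T2. No recall rate and no recall effect on STAI is given, so that remains a judgement. The argument also says little about the one-year test.
- **Size.** The precision gain is modest even on favourable assumptions. The 9.3-point scale is percent change, so the figures carry over only approximately to a model of the follow-up score.
- **Heterogeneity.** Nothing in the documents shows that the effect differs by density. The dilution figures are scenarios, and the interaction test would miss modest differences.
- **Covariates.** That the arm cannot alter density or result is a reasonable inference, but the documents do not say that image readers are unaware of arm.

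All of this stands, and it limits the point to a refinement. It does not remove the point: the plan still has no quantitative Aim 1 analysis that uses either variable.

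**Conclusion.** The point holds as an optional improvement, not as an error. The pooled contrast is valid and should remain primary.

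On the assumption of 10% recall with a 0.5 to 1.0 SD effect, adjustment is worth about 14 to 59 women per group at T2. The interpretive gain matters more. If a 9.3-point benefit were confined to dense women at 40% to 50% of the sample, the pooled test would have about 14% to 22% power, and the plan has no pre-specified breakdown that could separate this from no effect. A dense-only contrast would raise power for that effect to about 36% to 46%, which is better but still far from conclusive. The dense share, the recall share and the effect sizes are all assumptions.

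**What to change.** In the Analytic Approach for Specific Aim 1:

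1. Analyse follow-up STAI at each time point in a model with arm, baseline STAI, density category (dense or not) and screening result (normal or abnormal).
2. Keep the three overall arm contrasts at 0.017 as primary.
3. Pre-specify the arm-by-density interaction, and the arm contrasts within dense and within non-dense women, as supportive.
4. State how women without a completed mammogram are handled, since they lack both covariates.

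**Cost.** SAP wording only for the covariates, as the data are already abstracted. Moving from percent change to the follow-up score means that the detectable difference should be restated in STAI points, for which the documents give no SD. The within-dense contrasts (detectable difference about 13 to 15 points at a 40% to 50% dense share) and the interaction (about 16 to 18 points across dense shares of 30% to 70%) have low power. They must be labelled supportive, and a non-significant interaction should not be read as evidence of a uniform effect.
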